	9.3	CONFIDENTIALITY	
	9.4	INDEMNITY	
	9.5	Sponsor	
	9.6	Funding	
	9.7	Audits	
10		UDY MANAGEMENT	
11	L PUE	BLICATION POLICY	16
12	2 REF	FERENCES	17

CSP: Conduction system pacing CT: Computed tomography ECG: Electrocardiogram

EGG. Electrocardiogram
EGM: Electrogram
HBP: His-bundle pacing
ICE: Intracardiac echocardiogram
LBBB: Left bundle branch block LBP: Left bundle pacing
LBAP: Left bundle area pacing
LV: Left ventricle
LVAT: Left ventricular activation time

MRI: Magnetic resonance imaging

RV: Right ventricle

TOE: Transoesophageal echocardiogram TTE: Transthoracic echocardiogram

Study Summary

TITLE	Fluoroless Conduction System Implant		
DESIGN	Cohort observational study and interventional at validation phase		
AIMS	Define a feasible fluoroless protocol for conduction system lead implantation		
	Primary Outcomes:		
OUTCOME MEASURES	1. Success rate of conduction system lead implant Secondary Outcomes: 2. Fluoroscopy time 3. Total procedure time 4. Capture threshold 5. Number of times leads deployed 6. Complication rates: a. Lead implanted at the incorrect position: non-septal positions b. Lead displacement c. Lead injury d. Rise in threshold (late complication) e. Vascular injury f. Perforation with or without subsequent tamponade g. Device related infection h. Pneumothorax		

POPULATION	Patients with any indication for a pacemaker
ELIGIBILITY	Main Inclusion Criteria 1. Patients with a ventricular pacing indication: high grade atrioventricular block and symptomatic trifasicular or bifasicular block. (in order to assess the level of conduction system block) 2. Adults willing to take part (ages 18 – 100 years old) 3. Able to give consent.
	Main Exclusion Criteria 1. Unable to give consent 2. Children age < 18 years and adults > 100 years old 3. Pregnant patients 4. Pacing device in situ 5. Indication for cardiac resynchronisation therapy 5.
DURATION	1 year

1. Introduction

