1.1 Background

Discovering how to clinically deliver conduction system pacing efficiently could be a paradigm shift. Early work on conduction system pacing focused on the His bundle, with right atrial mapping for the His signal and deployment of a lumenless pacing lead(1). Left bundle pacing (LBP) then emerged as an alternative, approaching via the basal right ventricular septum to deploy a lead through the septum to capture the left bundle on the left side of the septum(2,3)

Current literature report improved left ventricular function, heart failure outcomes and mortality in conduction system pacing(4,5). Additionally, LBP has a larger target area, can be done with low capture thresholds, has better threshold stability and large amplitude R waves(3). Widespread roll out of conduction system pacing clinically, however, faces three major challenges.

Challenge A1: Identifying target area for lead deployment

Despite growing adoption, conduction system pacing implants remains challenging. Even experienced device consultants take time to learn the technique. Experienced centres achieve implant success of 95%, but centres with new conduction system implanters (but highly experienced pacemaker implanters) have rates as low as 56%(6,7).

Fluoroscopic interpretation is challenging, for several reasons. The target area is smaller than conventional right ventricular pacing, and can be even smaller when there is fibrosis in the septum. The chambers may well be dilated, which displaces not only the fluoroscopic position of the target, but also its orientation. The lead can also be difficult to advance, because of septal fibrosis, unrecognised lead entanglement and unclear trans-septal trajectory. Interpretation of surface ECG and lead data is not straightforward either: there are many levels in the conduction system at which block can occur and it is difficult to distinguish them confidently. Lead entanglement and mal-orientation may be detectable with elaborate equipment such as intracardiac echocardiography (ICE) but we do not know what fluoroscopic or electrical features might provide routine clinical operators with a timely warning. Previous approaches to address these issues have involved normal-heart cadaveric studies which do not give the electrical context of a clinical implant(8).

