1.2 Original Hypothesis

- Conduction system leads can be implanted with almost no fluoroscopy using electroanatomical mapping
- 2. Using electro-anatomical mapping will increase safety of conduction system lead implantation
- The procedure times with electro-anatomical mapping will be less than that of conventional methods using fluoroscopy

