1.3 Rational for Current Study

Currently conductions system pacing can have long fluoroscopy times when compared to conventional right ventricular pacing. This may be due to difficult cardiac anatomy, altered lead trajectory and obstacles such as entanglement, that is not readily visualised with fluoroscopy. As a result operators experience additional cumulative fluoroscopy times. Our study will devise a standardised implantation protocol using 3D electroanatomical mapping systems to reduce both fluoroscopy and procedure times.

2. Study Objectives

Primary Objective

The primary objective of this study is develop a fluoroless implant protocol of conduction system leads using 3D electroanatomical mapping.

Secondary Objective

The secondary objectives will be

- To reduce the overall procedure and fluoroscopy time with utilisation of targeted lead deployment.
- 2. Improve complication rates

3. Recruitment

A total of 75 patients will be recruited for the study

50 patients with a ventricular pacing indication (high grade atrioventricular block and symptomatic trifasicular or bifasicular block) for pacing will be recruited prospectively. The patients will be divided into two groups; 25 patients in the derivation cohort and 25 patients in the validation cohort. The derivation cohort will undergo a detailed research protocol to determine the optimised work flow and this will be applied prospectively to the validation cohort.

The success rates, procedure times, complication rates and fluoroscopy times will be assessed. The 25 patients undergoing conventional methods of conduction system pacing will be recruited as a control arm to compare these outcomes.

In summary, the 75 patients will be grouped as following; 25 patients in the derivation cohort, 25 patients in the validation cohort and 25 patients in the control arm.

4. Methodology

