4.2 Validation

25 patients will be recruited to the validation cohort.

An optimised work flow will be derived using the information collected from the derivation cohort. Namely, the target areas for FAM and electro-anatomical maps will be determined, and the successful pattern of lead septum interaction on CARTO will be defined.

The streamlined workflow will then be applied to 25 prospective patients. The success rates, procedure time, fluoroscopy time, capture threshold, number of attempted lead deployments and complication rates will be assessed.

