4.3 Control Arm

The control arm will consist of 25 patients undergoing a conduction system pacemaker using conventional pacing methods, with the same pacing indications as the study arm.

[figure not shown]

Figure 1: Recruitment workflow

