4.6 Study Outcome Measures

Primary Outcome Measures

1. Success rates of conduction system lead implant (fluoroless workflow vs conventional methods)

Secondary Outcome Measures

- Procedure and fluoroscopy times of the fluoroless workflow vs current conventional methods of His-bundle and Left-bundle pacing
- Procedure and fluoroscopy times of the fluoroless workflow vs conduction system implant to current right ventricular pacing
- 3. Assess capture threshold of His-bundle and Left-bundle pacing from the fluoroless workflow vs that of conventional methods of conduction system implantation
- 4. Number of times leads deployed in the fluoroless protocol vs conventional methods of conduction system implantation
- Complication rates in the fluoroless protocol vs conventional methods of conduction system implantation:

- a. Lead implanted at the incorrect position: non-septal positions
- b. Lead displacement
- c. Lead injury
- d. Rise in threshold (late complication)
- e. Vascular injury
- f. Perforation with or without subsequent tamponade
- g. Device related infection
- h. Pneumothorax

5 Participant Entry

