25 patients will provide the ability to determine the percentage of a successful implant with a precision of a SE (\pm 8%) of a success rate of approximately 80% SD of implant time = SD of total procedure time / $\sqrt{2}$ = 67 / $\sqrt{2}$ =47.37 SE = SD/ $\sqrt{\text{sample size}}$ = 47.37/ $\sqrt{2}$ 5 = 9.47

Data and all appropriate documentation will be stored for a minimum of 5 years after the completion of the study, including the follow-up period.

To assess the primary outcome of the success rates of the conduction system lead implant using the fluoroless workflow developed during our study, ECG information will be collected and capture will be determined by experts.

Fluoroscopy and procedural times will be analysed with one-way ANOVA. Success rates, capture thresholds and battery life will be analysed with t-test.

9 Regulatory issues

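### The comparative primary outcome is an expert reading of the ECG, with no masking to cohort, no separation from the implanters and no stated common reading of the control ECGs

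*Protocol*

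**What the plan says.** Protocol Section 4.6 makes the primary outcome comparative: "Success rates of conduction system lead implant (fluoroless workflow vs conventional methods"). Section 8 states how success will be established: "ECG information will be collected and capture will be determined by experts". The opening of that sentence refers only to the fluoroless workflow developed in the study and does not mention the control ECGs.

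The Study Summary describes the design as "Cohort observational study and interventional at validation phase". Section 3 sets the groups as "25 patients in the derivation cohort, 25 patients in the validation cohort and 25 patients in the control arm". The cohorts come in sequence: the workflow is built on the derivation patients, and then, in Section 4.2, "The streamlined workflow will then be applied to 25 prospective patients". For the comparator, Section 4.3 says "The control arm will consist of 25 patients undergoing a conduction system pacemaker using conventional pacing methods". No random allocation is described.

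The text does not mention masked reading, independent reading, the number of experts, their relation to the implanting team, or the criteria by which a tracing counts as capture.

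**The concern.** Section 8 settles the primary outcome by judgement and not by a stated measurement rule. The operators necessarily know which method they used. The team that develops the workflow also tests it. The experts are not defined, so as written they could include the implanters or other members of that team.

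Two routes to bias are left open:

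- A reader who knows the cohort may resolve a doubtful tracing in the direction expected.
- The control ECGs may be read by other people, or to another standard, because the Section 8 sentence covers only the fluoroless workflow. Ascertainment could then differ between arms without anyone intending it.

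Either would appear as a difference in success rates that the method did not cause. The procedure cannot be masked. A surface ECG recorded at the final lead position can be, because it does not show whether mapping or fluoroscopy guided the lead.

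**Working it through.** **Inputs.** From Section 8: 25 patients per group, success of about 80%, standard error (SE) of ±8%, and a t-test for success rates. The comparison is taken as validation against control. Two-sided alpha of 0.05 is my assumption, as the protocol states none. The reader-bias fractions in step 4 are also assumptions, because the documents give no reader-error rate.

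**1. The protocol's own figure.** SE = √(0.8 × 0.2 / 25) = 0.080, or 8 points. This reproduces.

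**2. Weight of one tracing.** 1/25 = 4 points, half the stated SE. Two tracings in one arm move its rate by 8 points, one full stated SE. The SE of the difference between two arms at 80% is √(2 × 0.8 × 0.2 / 25) = 0.113, or 11.3 points.

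**3. Reclassification from equal results.** Start at 20/25 in both arms and re-read k workflow failures as successes:

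| k | Workflow vs control | t-test p | Fisher p |
|---|---|---|---|
| 1 | 84% vs 80% | 0.72 | 1.00 |
| 2 | 88% vs 80% | 0.45 | 0.70 |
| 3 | 92% vs 80% | 0.23 | 0.42 |
| 4 | 96% vs 80% | 0.085 | 0.19 |
| 5 | 100% vs 80% | 0.018 | 0.050 |

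The t-test falls below 0.05 only when all five workflow failures are overturned. If two tracings move up in one arm and two down in the other, 22/25 against 18/25 differs by 16 points, t = 0.16/0.113 = 1.41 and p is about 0.16.

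**4. False-positive rate under assumed reader bias.** Let the true rate be 80% in both arms. A fraction f of workflow failures is read as capture and a fraction g of control successes is read as failure. The observed rates are then 0.8 + 0.2f and 0.8(1 − g). Exact enumeration of two binomial arms of 25 with the t-test gives:

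| f | g | Observed rates | False difference | False-positive rate |
|---|---|---|---|---|
| 0 | 0 | 80% vs 80% | 0 points | 5.5% |
| 10% | 0 | 82% vs 80% | 2 points | 5.9% |
| 25% | 0 | 85% vs 80% | 5 points | 8.0% |
| 50% | 0 | 90% vs 80% | 10 points | 17.4% |
| 10% | 10% | 82% vs 72% | 10 points | 14.0% |
| 25% | 10% | 85% vs 72% | 13 points | 21.0% |
| 50% | 10% | 90% vs 72% | 18 points | 38.9% |

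The table shows sensitivity only and does not predict the bias. Modest bias in one arm distorts the estimate more than the test. The false-positive rate rises markedly only when the bias is large or runs in opposite directions in the two arms.

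**The case against.** The strongest reply is that this is silence, not a stated error. The protocol does not say that the experts know the cohort or implanted the leads, and an analysis plan or reading manual may cover the matter. The first part stands: a reader might infer that the protocol has the implanters judge their own cases unmasked, and the text does not say so. The second part does not dispose of the point. Who reads the primary endpoint, and what they know when they read it, is study conduct to be fixed before any tracing is read. Section 8 does set out the assessment, and as written it permits unmasked reading.

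Other objections are right and limit the point:

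- Section 1.1 says "Interpretation of surface ECG and lead data is not straightforward either", and a reader might take this as an admission that capture readings are equivocal. The sentence goes on to the difficulty of telling levels of block apart, within a discussion of finding the target area. It does not concern confirmation of capture after deployment.
- A reader might infer a declared expectation of higher success. The hypotheses in Section 1.2 concern fluoroscopy ("Conduction system leads can be implanted with almost no fluoroscopy using electroanatomical mapping"), safety and procedure time. None predicts higher success. Only the general remark in Section 1.1 that mapping can overcome the implant challenges leans that way.
- A reader might conclude that a few tracings decide the comparison. The 16-point shift is an assumed scenario: it overturns two of about five workflow failures while control readings move the other way, and still gives p of about 0.16. Some failures cannot be re-read at all, since Section 4.5 foresees leads that cannot be implanted.
- Electrograms (EGMs), mapping data or the multi-site pacing recordings of derivation patients (Section 4.1) could reveal the cohort. Derivation results are also needed before the workflow is fixed. Both affect how masking is done, not whether it is possible for the final-position surface ECG.

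**Conclusion.** The point holds as a weakness in how the primary outcome is ascertained. Followed as written, Section 8 allows expert judgement without masking to cohort, without separation from the implanters and without a stated common reading for controls, in a non-randomised comparison where operators know the method. That leaves the success rates open to detection bias.

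The documents cannot give its size. The firm figure is 4 points per reclassified tracing, half the stated SE. One or two would shift the estimate but would rarely create significance alone. The false-positive rates rest on assumed bias fractions, equal true rates of 80% and an assumed two-sided 0.05 level. The study is not invalidated, and confounding between the groups is a separate problem that masking does not touch. The change should be made because the risk falls on the primary comparison and is cheap to reduce.

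**What to change.** In Section 8, state that:

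1. The planned experts judge capture from de-identified final-position surface ECGs of the validation and control patients. Derivation patients are included too, and re-read if their tracings were already read to set the workflow.
2. Tracings are read in random order, masked to cohort and operator, against one set of capture criteria fixed beforehand for all groups.
3. No expert reads a case they implanted, where the existing panel allows it.
4. This reading is locked before any EGM, mapping or procedural data that could reveal the cohort are seen.

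The cost is relabelling and shuffling the tracings, and a second reading of the derivation ECGs. No patient procedure is added. Whether the panel can avoid reading its own cases cannot be judged from the protocol, which gives neither the number of experts nor their link to the implanters. If masked reading is already intended, writing it into Section 8 settles the point.

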The CartoMerge module will be used to expedite anatomical mapping using the MRI data collected.

- 5. The mapping catheter will be removed and an intracardiac echo (ICE) catheter, will be inserted through the femoral vein.
- 6. The conduction system pacing lead will be inserted through the axillary vein. A right atrial lead will be inserted into the right ventricular apex for back up pacing in the instance the conduction system is bumped. The basal-septum, mid-septum, high-septum and anterior walls will be paced to identify electrical markers for optimal implant sites.
- 7. The lead will be visualised on the Carto maps created.
- 8. The lead will be deployed at the predetermined target site under direct visualisation using the ICE catheter. Through direct visualisation, three key determinants can be assessed:
 - 1. Lead trajectory through the septum with the goal of achieving perpendicularity
 - Lead septum interaction and whether there is evidence of entanglement preventing lead progression.
 - Relationship between the sheath and lead that can lead to or prevent failure of lead deployment.
- 9. Once the conduction lead is secured the right atrial lead will be pulled back and secured in the right atrium.
- 10. The procedure will be completed as per standard clinical implant protocol with routine clinical follow-up thereafter:

The information from echocardiography will be corroborated with the lead-septum interaction visualised on electro-anatomical maps created on CARTO.

In this cohort of patients, the conduction system lead will initially pace the His-bundle then the left bundle in order to collect data for both methods of physiological pacing. The information collected from ICE and electro-anatomical mapping will be used to develop a streamlined workflow that will map targeted areas, where challenging implant sites will be rapidly identified (such as areas of scar), reducing the number of attempted lead deployments and visualise lead-septum interaction, apposition and progression, improving safety parameters.

At the end of the procedure, the lead position will be documented with a very short, *single fluoroscopic acquisition*. This remains integral for future comparison in the instances of lead complications and in particular lead displacement.

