4.5 Burden/Risk

The main burdens for the patient include:

- The extra time taken to perform the experiments and experimental procedures during their scheduled clinical procedure due to the additional diagnostic investigations. The right heart electro-anatomical mapping will add 10 minutes. The echocardiography will add an additional 5 minutes.
- 2. The extra access in the groin for the mapping catheter and ICE catheter.
- 3. Patients receiving unconventional therapy with conduction system lead implantation

Control Group C: N=25 (Standard of care) I. 12-lead ECG Before the Echocardiogram procedure 3. MRI of the heart I. 12-lead ECG During the 2. Fluoroscopy procedure (x-ray) Routine clinical ca Follow-up 6 weeks, 6 months, 1 v Deleted:

The burden will be mitigated by the minimum extra time being used to complete the experiments, the use of local anaesthetic and the immediate removal of extra research related sheaths as soon as they are not needed

The main risks for the patient are:

A conduction system pacing wire is not known to have a higher complication rate compared to a conventional pacing wire. Conduction system pacing wires have been shown to be as effective as conventional pacing wires at preventing slow heart rates and improving heart pumping. If a complication occurs and the conduction system pacing wire cannot be implanted or does not perform as expected during follow-up a procedure will be performed to convert your pacing system to a conventional pacing system.

The additional risks of vascular tube placement include:

- 1% risk of bruising around the area
- 1 in 1000 risk of damage to the blood vessels requiring surgery
- Less than 1 in 500 risk of stroke

The additional risks of intracardiac echocardiogram include

- 1% risk of bruising around the access area in the leg
- Less than 1 in 1000 risk of heart perforation

The additional risks of electro-anatomical mapping include

Less than 1 in 1000 risk of heart perforation

Therefore, the overall risk of serious complications arising from taking part in the research study are less than 4 in 1000 (0.4%)

Pacemaker implantation involves exposure to ionising radiation to visualise lead implantation. Taking part in this study involves exposure to additional exposure to radiation above the standard clinical procedure due to the additional measurements that will be taken.

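### The one-way ANOVA in section 8 for fluoroscopy and procedure times most naturally includes the derivation cohort, which never receives the workflow, so it does not answer the two-group question in section 4.6

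*Protocol*

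**What the plan says.** Section 3 of the protocol recruits 75 patients in three groups of 25. On the first two it says: "The derivation cohort will undergo a detailed research protocol to determine the optimised work flow and this will be applied prospectively to the validation cohort". On the third: "The 25 patients undergoing conventional methods of conduction system pacing will be recruited as a control arm to compare these outcomes". Section 4.3 then sets the controls beside a single study arm, without saying whether that arm is one cohort or both.

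Section 4.1 describes what derivation patients undergo:

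- Broad right-heart anatomical, voltage and activation mapping.
- A catheter exchange: "The mapping catheter will be removed and an intracardiac echo (ICE) catheter, will be inserted through the femoral vein".
- Multi-site pacing: "The basal-septum, mid-septum, high-septum and anterior walls will be paced to identify electrical markers for optimal implant sites".
- Pacing of both targets: "the conduction system lead will initially pace the His-bundle then the left bundle in order to collect data for both methods".

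Section 4.2 derives the streamlined workflow from these data, applies it to the 25 validation patients, and lists the outcomes to be assessed. Section 4.5 gives the added time: "The right heart electro-anatomical mapping will add 10 minutes. The echocardiography will add an additional 5 minutes".

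Section 4.6 frames the primary outcome and most secondary outcomes as the fluoroless workflow against conventional conduction system implantation. One further item brings in right ventricular pacing for the times. On analysis, section 8 says: "Fluoroscopy and procedural times will be analysed with one-way ANOVA". It assigns a t-test to success rates, capture thresholds and battery life. No groups are named for either test.

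**The concern.** The workflow does not exist until the derivation cohort has been completed, so derivation procedure times describe a research procedure. If that cohort is one of the ANOVA groups, the omnibus test can reach significance because the research procedure took longer, whatever the workflow does. A non-significant result would be no clearer, because the test spreads its attention over three groups when only two bear on the question.

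The third hypothesis in section 1.2 is that mapping-guided procedures are shorter than conventional ones, and procedure time is the outcome that tests it. The protocol has named a test for that outcome which does not isolate the comparison of interest.

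A second, weaker worry concerns the remaining outcomes. The wording of sections 3 and 4.3 does not exclude derivation patients from the comparison with controls. In a study that describes no randomisation, that leaves a choice between 25 versus 25 and 50 versus 25 which could be made after the results are seen.

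**Working it through.** **Inputs.** From section 8: n = 25 per group, SD of total procedure time 67 min, SD of implant time 67/√2. From section 4.5: 10 min for mapping and 5 min for echocardiography. Assumed: alpha 0.05, since the protocol gives none; equal SD in the three groups; validation and control with the same mean.

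**Reproducing the protocol's own figures.**

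- SD of implant time = 67/√2 = 47.38 min (printed as 47.37).
- SE of the mean = 47.38/√25 = 9.47 min, as stated.
- SE of an 80% success rate = √(0.8 × 0.2/25) = 0.08, as stated.

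**Which groups fit a one-way ANOVA?** Two readings are open.

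- Derivation, validation and control: these are exactly the three recruited groups.
- Fluoroless, conventional and right ventricular pacing: section 4.6 mentions all three, but section 3 recruits no right ventricular pacing group.

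The first reading needs nothing that the protocol does not supply, so it is the natural one.

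**How often the three-group test rejects when only derivation differs.** Let derivation be longer by d minutes and the other two means be equal. The three means then lie 2d/3, −d/3 and −d/3 from the grand mean, and their squares sum to 2d²/3. The noncentrality parameter is λ = 25 × (2d²/3)/SD². Rejection is the probability that a noncentral F with 2 and 72 degrees of freedom exceeds the 5% critical value.

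For d = 15: 2 × 225/3 = 150, and 25 × 150 = 3750. With SD² = 67²/2 = 2244.5, λ = 1.67. With SD² = 67² = 4489, λ = 0.84.

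| Extra derivation time d | SD 47.4 min | SD 67 min |
|---|---|---|
| 5 min (echocardiography only) | 6.4% | 5.7% |
| 10 min | 10.8% | 7.8% |
| 15 min (both timed steps) | 18.8% | 11.5% |
| 30 min (assumption) | 61.4% | 34.1% |

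The reference value is 5%. The 15 min is an upper figure for the two timed steps, because some mapping remains in the streamlined workflow. The multi-site pacing and the His-then-left-bundle sequence are not timed in the document and would come on top. The 30 min row shows sensitivity to them and has no source in the protocol. No SD is given for fluoroscopy time, so the same calculation cannot be made for it.

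**Precision with two groups only.** SE of the difference, validation versus control:

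- 47.38 × √(1/25 + 1/25) = 13.4 min
- 67 × √(1/25 + 1/25) = 19.0 min

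If derivation and validation were combined (50 versus 25):

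- 47.38 × √(1/50 + 1/25) = 11.6 min
- 67 × √(1/50 + 1/25) = 16.4 min

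**The case against.** The best defence is that the protocol never says the derivation cohort is compared with controls. Section 4.2 lists the outcomes straight after applying the workflow to the validation patients. Section 8 ties the primary outcome to the workflow developed in the study, which derivation patients cannot have received. The precision figures use 25 patients, not 50. The t-test for success and thresholds fits validation against control. The ANOVA groups are unnamed, and naming them could be left to a statistical analysis plan.

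Much of this stands, and it rules out stronger readings that a reader might infer:

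- **That derivation and validation are pooled.** No section says so, and a three-group ANOVA would keep them apart. A shift of 15 × 25/50 = 7.5 min in a pooled fluoroless mean would follow only from an analysis that the protocol does not propose. Even then it would be the most that the two timed steps could cause, not a minimum.
- **That lead deployments and thresholds are distorted in the same way.** The ANOVA sentence covers times only, and no test is named for deployments. Section 4.1 speaks of pacing the two targets in turn and does not say that this needs an extra fixation.
- **That research steps alone determine derivation procedure times.** They add to them. The implant itself and the mapping shared with the workflow contribute as well.

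What does not stand is the appeal to a later plan. The protocol has already chosen the test by name, and that choice fits three groups where section 4.6 asks about two. A planned validation-versus-control contrast within the ANOVA would answer the question, but the protocol specifies none.

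**Conclusion.** The point holds for fluoroscopy and procedure times. On its natural reading, section 8 tests three groups, one of which did not receive the workflow, to answer a question about two. With validation and control identical, a 15 min excess in derivation alone would produce a significant result in about 19% of trials at SD 47.4 min and about 12% at SD 67 min, in place of 5%. The second figure uses the SD that the protocol gives for total procedure time. The sizes rest on alpha 0.05, equal SDs and all 15 min being specific to derivation; at 5 min the inflation nearly disappears.

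For the other outcomes there is an ambiguity and no demonstrated error. Sections 3 and 4.3 do not exclude derivation, while section 4.2 and the primary-outcome sentence in section 8 lean towards validation.

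**What to change.** State in sections 4.6 and 8 that every contrast of the fluoroless workflow with conventional conduction system implantation is validation (n = 25) versus control (n = 25). This covers success, procedure and fluoroscopy times, thresholds, deployments and complications. Replace the ANOVA for times with that two-group comparison. Report the derivation cohort descriptively.

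If the ANOVA was meant to bring in right ventricular pacing, name that group and say where its data come from, since none is recruited.

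The change is wording only. Its cost is that derivation patients add no numbers to the comparison: the SE of the time difference is 13.4 min, against 11.6 min if the cohorts were pooled (19.0 against 16.4 min at SD 67). That is a fair price, because the narrower figure would describe a mixture of the workflow and the research procedure.
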